Planned study period	
Expected start date of inclusion: April 2013
 
Expected completion date of inclusion: April 2016
 
Expected completion date: July 2018

I. OBJECTIVES OF THE TRIAL

I.1 Main objective

Evaluate the investigator-assessed 9-month progression-free survival rate (according to RECIST 1.1 criteria).

I.2 Secondary objectives

Tolerance to treatment

Response rate according to RECIST 1.1 criteria at 9 months

Response rate according to EASL criteria, assessed at 9 months, by centralized review

Hepatic progression-free survival according to RECIST 1.1

Overall survival

Progression-free survival

Secondary resection rate

Evolution of tumor marker levels

II. PATIENT SELECTION

II.1 Inclusion criteria

Inclusion in the study requires that all of the inclusion criteria listed below be met:

- Histologically proven colorectal adenocarcinoma
- Radiologically or histologically proven liver metastases
- At least one measurable liver lesion according to RECIST v1.1 criteria
- Age \geq 18 years
- WHO Index \leq 2
- Life expectancy \geq 3 months
- No extra-hepatic disease, except pulmonary nodules if number \leq 3 and size $<$ 10 mm each
- Hepatic invasion $<$ 60%.
- Primary tumor resected or in place
- No prior chemotherapy for metastases (except peri-operative chemotherapy, if the last cycle was given at least 12 months ago)
- Adjuvant chemotherapy after resection of the primary site allowed if the last cycle was administered at least 12 months ago
- Normal liver function: total bilirubin \leq 1.5N, AST \leq 5N, ALT \leq 5N and PAL \leq 5N.

- TP \geq 60%
- Adequate hematologic function: PNN \geq 1500/mm³ , platelets \geq 100,000/mm³ , Hb \geq 9g/dL
- Good renal function: creatinine clearance \geq 60 mL/min
- No cardiac dysfunction: no cardiovascular events in the past 6 months or no NYHA \geq 2.

II.2 Non-inclusion criteria

Inclusion in the study requires that none of the non-inclusion criteria listed below are present:

- Patient eligible for curative treatment (resection and/or radiofrequency ablation) as determined by the PCR (including the opinion of a liver surgeon)
- Pregnant or breastfeeding women or patients of either sex of childbearing age who are not using an adequate method of contraception (see section V. 4)
- Previous cancer, except for non-melanoma skin cancers and curatively treated cervical in situ cancers. Other curatively treated cancers are allowed provided they have not recurred for more than 5 years

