- Peripheral neuropathy
- Inflammatory bowel diseases
- Intestinal occlusion
- Chronic liver disease (viral, alcoholic or metabolic)
- Immunodeficiency syndromes (transplant history, HIV infection)
- Known contraindications to 5FU, oxaliplatin, folinic acid, irinotecan or contrast media
- Patient with known contraindication to liver embolization procedures:
 - Presence of bilio-digestive anastomoses or biliary prosthesis
 - Cruciate or tumor thrombosis of the portal vein
- Patient who for psychological, social, family or geographical reasons could not be followed regularly
- Legal incapacity (persons deprived of liberty or under guardianship)
- Patient not affiliated with a social security plan.
- Concurrent participation in another study investigating the effect of a treatment until 4 weeks after the end of this study.

III. PRE-INCLUSION ASSESSMENT

To be performed within 21 days prior to treatment and before inclusion:

- Thoracoabdomino-pelvic CT scan, documenting at least one measurable liver lesion
- Hepatic MRI
- PET scan strongly recommended before inclusion.

Remember to keep the radiology CDs in the patient's file; the ARC FFCD will make a copy of these imaging studies.

To be completed within 14 days prior to inclusion:

- Complete clinical examination including: weight, height, vital signs, WHO index, pain assessment (VAS)
- Medical history
- Description of the disease
- Biological workup consisting of measurements of hematological, nephrological and hepatic parameters: CBC/platelets, blood ionogram, creatinine, albumin, transaminases (AST, ALT), alkaline phosphatases (ALP), total and conjugated bilirubin, PT, APTT, fibrinogen level
- Determination of lipase
- ACE and CA 19-9 assay
- KRAS status will be determined at each center but not routinely at inclusion
- **Fasting** sample for patients participating in the 'lipid' translational study; don't forget to perform it (according to the corresponding section, p25).

IV. INCLUSION

After the patient has signed the clinical consent form (Appendix 1) and the results of the examinations necessary for inclusion in the study have been verified, the patient can be included. For centers participating in the associated 'lipid' study, the specific information and consent form (Appendix 2) must be proposed.

[figure not shown]

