The primary endpoint will be the proportion of patients alive without progression (death will be considered as progression) at 9 months after the start of treatment according to RECIST V1.1 criteria, as assessed by the investigator.

Progression-free survival time will be defined as the time interval between the date of inclusion and the date of progression or death (regardless of cause). For patients alive without progression, the time interval between the date of inclusion and the date of last morphological evaluation will be taken.

XII.2.2 Secondary Criteria

The secondary endpoints will be:

- Tolerance to the treatment
- Response rate according to RECIST v1.1 criteria at 9 months (according to the investigator)
- Response rate according to EASL criteria (assessed by centralized review) at 9 months
- Hepatic progression-free survival according to RECIST v1.1 criteria at 9 months
- Overall survival
- Progression-free survival
- The rate of secondary resections
- Changes in tumor marker levels

Liver progression-free survival will be defined as the time interval between the date of inclusion and the date of liver progression as assessed by the investigator's RECIST V1.1 criteria or death (regardless of cause) or the date of the last morphological assessment for patients alive without progression.

Overall survival will be defined as the time interval between the date of inclusion and the date of death regardless of the cause of death or the date of last news for living patients.

Tolerance to treatment will be assessed by:

- duration of treatment, doses received, dose reductions and deferrals
- Toxicities collected at each monthly visit, and described according to NCI-CTC version 4.0 criteria; Grade 3, Grade 4 and Grade 5 toxicities will be reviewed
- the number and description of SAEs

Changes in tumor marker levels (CEA and CA 19-9) will be assessed throughout the study.

XII.3 Calculation of the number of subjects needed

A 1-step Fleming design will be used, with a one-sided α risk of 5% and a power (1- β) of 90%.

The assumptions are:

- H0: A proportion of patients living without progression of 55% during the first 9 months is uninteresting;
- H1: A proportion of patients living without progression of more than 55% during the first 9 months would show the interest of the treatment; a proportion of 75% is hoped for.

Total number: **48 evaluable patients**

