5.1 Definition of analysis populations

5.1.1 Intent-to-treat (ITT) population

The intention-to-treat population is defined as all patients included in the study, regardless of eligibility criteria.

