6.5 Statistics

The confidence intervals provided will be two-sided 95% confidence intervals except for the primary endpoint where the calculated confidence interval will be a one-sided 95% confidence interval.

Quantitative data will be described using the following descriptive statistics: number, mean, standard deviation, median, first and third quartile, and minimum and maximum. These statistics will be considered the usual statistics for the analysis of quantitative variables. Quantitative variables can be categorized using their median or a cut-off known from the medical literature.

Categorical variables will be summarized, using the following descriptive statistics: the number, frequencies and percentages for each level of the variable. These statistics will be considered as the usual statistics for the analysis of categorical variables.

When necessary, the 95% confidence intervals for the proportions can be calculated from the exact binomial distribution.

Survival data will be estimated and plotted using the Kaplan Meier method (Kaplan and Meier, 1958). They will be described by the median and rates calculated at different time points with their two-sided 95% confidence intervals. The confidence intervals for the rates will be constructed from the Greenwood variance calculated using the log-log transformation.

The median follow-up time will be estimated by the reverse Kaplan-Meier method (Shemper, 1996).

As an exploratory measure, for the uni and multivariate analyses, the hazard ratios will be estimated using a Cox model (Cox, 1984). The hypothesis of proportionality of the rates will be tested using the graphical representation and the test based on Schöenfeld's residuals (Grambsch, 1994); the linearity of the effect of the continuous variables on the risk will be evaluated from the graphical representation of the martingale residuals. Confidence intervals for the coefficient estimates of the Cox models will be calculated using the Wald method.

7 Statistical analysis

	Population ITT	Population ITTm	Tolerance population	Population Per protocol
Description of Baseline				
Eligibility criteria for inclusion	X	X		X
Demographic characteristics	X	X		X
Clinical characteristics at inclusion	X	X		X
Biological characteristics at inclusion	X	X		X
Characteristics related to the disease	X	X		X
Median follow-up time	X	X		X
Main criterion				
Progression-free survival rate at 9 months	X	X		X
Secondary criteria				

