Overall survival, progression-free survival	X	X		X
Progression-free survival at 9 months	X	X		X
Response rate (RECIST) at 9 months	X	X		X
Response rate (EASL) at 9 months (centralized review)	X	X		X
Secondary resection rate	X	X		X
Evolution of tumor marker levels	X	X		X
Tolerance				
Administration of the treatment (duration, dose received ...)			X	
Toxicities			X	
Exploratory analysis	X	X		X

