7.4.9 Evolution of tumor marker levels

7.4.9.1 Definition

The evolution of tumor markers (CEA and CA19-9) will be evaluated throughout the study, from inclusion to progression. It will be described at each evaluation.

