7.4.9.2 Evaluation

The delta for CEA and CA19-9 (value at assessment - value at baseline/value at baseline) *100 will be described at each assessment and plotted as a boxplot.

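### SAP 7.4.9.2 pools percent change in CEA and CA 19-9 over all patients, so normal baselines dilute the marker response and the result depends on how many there are

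*SAP*

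**What the plan says.** SAP 7.4.9.1 sets the scope: "The evolution of tumor markers (CEA and CA19-9) will be evaluated throughout the study, from inclusion to progression". SAP 7.4.9.2 defines the measure as percent change from baseline, which "will be described at each assessment and plotted as a boxplot". For quantitative variables SAP 6.5 prescribes "number, mean, standard deviation, median, first and third quartile, and minimum and maximum".

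SAP 7.4.9 has no population line. The analysis table at the start of SAP section 7 has a row "Evolution of tumor marker levels", marked for the ITT, modified ITT and per-protocol populations. None of these is defined by marker level. For ITT, SAP 5.1.1 says: "The intention-to-treat population is defined as all patients included in the study, regardless of eligibility criteria". The modified ITT (5.1.2) depends on treatment given and on having an assessment; the per-protocol set (5.1.4) depends on the planned DEBIRI sessions and eligibility.

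Protocol XII.2.2 adds only: "Changes in tumor marker levels (CEA and CA 19-9) will be assessed throughout the study". In protocol II.1 measurability rests on imaging ("At least one measurable liver lesion according to RECIST v1.1 criteria"). The markers are measured before inclusion (protocol III, "ACE and CA 19-9 assay") and described at baseline (SAP 7.1.4). Neither document gives an upper limit of normal for either marker, or a separate display for patients below it.

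**The concern.** In a patient whose marker is raised, the ratio to baseline carries information about the tumour. In a patient whose marker is normal, it mostly reflects assay and biological variation around 1. A move from 1.5 to 3 (+100%) enters the same summary as a fall from 500 to 50 (-90%).

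Pooling the two groups mixes two distributions. The resulting median and quartiles then describe who was enrolled as well as how markers behaved under treatment. Two cohorts with the same response in raised-marker patients would report different marker results if their shares of normal baselines differed. At stake is the interpretability of one descriptive secondary endpoint.

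**Working it through.** The plan states no figure for the marker analysis, so there is none to reproduce. The check has a textual part and an illustrative calculation. SAP 7.4.9.2 is read as the usual percent change, 100 × (value − baseline) / baseline.

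**Text.** The entry criteria, the three population definitions, the two marker sections of the SAP and protocol XII.2.2 contain no baseline threshold. The nearest provision is in SAP 6.5, which allows quantitative variables to be categorised at their median or at a literature cut-off. It is optional and does not restrict this analysis.

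**Size.** Let f be the share of patients normal at baseline and R the ratio to baseline, so that the change is 100 × (R − 1). All inputs are assumptions, because the documents give none of them:

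- raised at baseline: log R normal, median R 0.30, SD 0.9
- normal at baseline: log R normal, median R 1.0, SD 0.4
- f = 0, 20, 40 or 60%

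The pooled distribution is

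P(R ≤ r) = f × Φ(ln r / 0.4) + (1 − f) × Φ((ln r − ln 0.30) / 0.9).

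For the median at f = 0.40, put r = 0.59: 0.4 × 0.094 + 0.6 × 0.774 = 0.50, a change of -41%. For the upper quartile at f = 0.20, put r = 0.81: 0.2 × 0.299 + 0.8 × 0.865 = 0.75, a change of -19%. Solving in the same way throughout:

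| Share normal at baseline | Lower quartile | Median | Upper quartile | Mean | SD (points) | Fall of at least 50% |
|---|---|---|---|---|---|---|
| 0% | -84% | -70% | -45% | -55% | 50 | 71% |
| 20% | -81% | -60% | -19% | -42% | 55 | 58% |
| 40% | -75% | -41% | +1% | -30% | 57 | 45% |
| 60% | -61% | -22% | +14% | -17% | 57 | 31% |

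The response in raised-marker patients is identical in every row; only the mix changes.

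**Sensitivity.** With a weaker assumed response in raised-marker patients (median change -60%, log-SD 0.8) and a 30% coefficient of variation in the others, the median goes from -60% to -49, -40, -30 and -22% at f = 20, 30, 40 and 50%. The upper quartile goes from -31% to -10, -2, +4 and +8%. Direction and rough size agree.

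The share at which the upper quartile reaches zero is f = (0.25 − p) / (0.5 − p), where p is the chance of a rise in raised-marker patients. With log-SD 0.8 it is 42, 33 and 19% for medians of -70, -60 and -50%; with log-SD 1.0 and a median of -60% it is 22%. It does not depend on the noise in normal-baseline patients, provided their median change is zero.

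**The case against.** The strongest reply is that this is a choice and not an error. The protocol endpoint is change in marker levels, and the SAP describes exactly that in the included patients, by marker and by assessment. No test, confidence interval or decision rule is attached to it. Restricting to raised baselines answers a different question. This stands, and it limits the weight of the point: the planned summary is correct for its own target but less informative than it could be.

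The plan also softens the problem. SAP 6.5 asks for the median and quartiles as well as the mean, the boxplot shows the distribution, and baseline markers are described. None of this separates the two groups.

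A reader might infer three stronger things that the material does not support:

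- **Small baseline values dominate the mean and SD.** In the calculation above the SD rises only from 50 to 57 points, and normal-baseline patients are the less variable group (SD 45 against 50 points). The effect is ordinary mixing. The model contains no absolute baseline values, so it cannot show instability from small denominators.
- **The upper part of the distribution reverses.** At 20% normal baselines the upper quartile is still -19%, and at 40% it is only +1%. A change of sign depends on assumed inputs. The 95th percentile is already +32% with no normal baselines, so a positive tail is not in itself a product of them. The median stays negative throughout.
- **A comparison of CEA with CA 19-9 is spoiled.** The SAP plans no such comparison.

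**Conclusion.** The point holds as one of dilution. Followed as written, SAP 7.4.9.2 pools patients in whom the marker is informative with patients in whom it largely is not, and its median and quartiles understate the response in the former. The direction follows from the text once it is accepted that a marker normal at baseline varies around no change and that some patients are normal at baseline.

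The size cannot be fixed from the documents. Under the main assumptions the median is about 10 points closer to zero at 20% normal baselines (-70 to -60%), 29 points at 40% and 48 points at 60%. These figures rest wholly on the assumed share, medians and log-SDs.

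This is a desirable improvement to a descriptive secondary endpoint, not a flaw in the design. The nine-month progression-free rate and its decision rule are untouched.

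**What to change.** In SAP 7.4.9.2, for CEA and CA 19-9 separately:

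- Give the percent-change summary (median and quartiles, with N at each assessment) and the boxplot for patients above the upper limit of normal at baseline.
- For patients normal at baseline, report N and the number who later rise above the limit, so that nobody drops out of the report.
- Keep the all-patient summary as supportive if wanted. Showing the ratio to baseline on a log scale is optional.

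The cost is SAP wording, a normal limit for each marker (from the laboratories, or a literature cut-off of the kind SAP 6.5 already allows), and fewer patients in the main marker table. Baseline values are already collected. SAP 4.5 allows adjustments in defined circumstances and requires them before the database is frozen; the subset should be fixed by then.

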7.5 Assessment of tolerance

Population:

Tolerance to treatment will be assessed by:

- Duration of treatment, doses received, dose decreases, and deferrals;
- Toxicities described according to NCI-CTC version 4.0 criteria;
- Number and description of SAEs

7.5.1 Chemoembolization

Chemoembolization therapy (CHE) will be described by:

- The number of HEC performed per patient and the total number of HEC performed by type of treatment. Causes will be described for patients who did not have the total number of HECs as per the protocol.
- The number and percentage of patients who had 1 HEC, 2 HEC, 3 HEC or 4 HEC according to the type of treatment (uni-lobar or bi-lobar)

- The type of treatment, the lobe involved, the dose of irinotecan administered. Causes will be described when the dose of irinotecan was not administered completely.
- The number of HEC deferrals and the causes of deferrals
- The number and percentage of patients treated with G-CSF

The consequences of treatment will also be described:

- The length of hospitalization
- The number and percentage of patients who experienced side effects during the procedure. A listing of other side effects during the procedure will be reported.
- Number and percentage of patients with pain >3 (VAS)
- The pain assessment (VAS) before HEC and within 24 hours after HEC will be described by grade (frequency of VAS for all HEC).

7.5.2 Administration of FOLFOX

7.5.2.1 Duration of treatment

The duration of the treatment will be described by:

- The number of treatments per patient;
- The duration of treatment (converted to months) will be calculated by the formula:

$$\text{Start date of last treatment} - \text{start date of first treatment} + 1 \text{ day}$$

Therapeutic breaks and any deferral days during this period will not be subtracted from this duration.

It will be described according to the usual descriptive statistics.

7.5.2.2 Doses administered

- The average number of treatments will be carried over.
- Compliance will be calculated according to the formula :

$$(\text{Cumulative dose received (in mg)} / \text{theoretical protocol dose (in mg)}) \times 100$$

The protocol doses of treatment are :

Oxaliplatin = 85 mg/m².

5FU bolus = 400 mg/m²

Continuous 5FU = 2400 mg/m².

Folinic acid = 400mg/m².

Compliance will be described by molecule according to the usual descriptive statistics.

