Study design and treatment plan	
Microbeads (100-300μm), loaded with irinotecan (DEBIRI). The maximum dose per procedure is 100 mg of irinotecan, combined with intravenous FOLFOX.
 
For patients with unilobar or bilobar liver involvement, DEBIRI will be injected at D17 and D45 (after the 2nd and 4th cycle of systemic chemotherapy with FOLFOX).
 
Patients with bilobar involvement but for whom the investigator decides that the treatment will be unilobar and sequential, there will be 4 sessions. Thus, the right and left livers will be treated alternately. The DEBIRI administrations will then be performed at D17, D31, D45, D59, or in case of a shift in chemotherapy treatment, after the 2^{ème}, 3^{ème}, 4^{ème} and 5^{ème} cycle of FOLFOX.
 
FOLFOX will be administered every 2 weeks until progression or unacceptable toxicity.

Statistical methods	
A 1-step Fleming design will be used, with a one-sided α risk of 5% and a power (1-β) of 90%.
 
The assumptions are:
 
 • H0: A proportion of patients living without progression of 55% during the first 9 months is uninteresting; • H1: A proportion of patients living without progression of more than 55% during the first 9 months would show the interest of the treatment; a proportion of 75% is hoped for.

	
Total number: 48 evaluable patients
 
Taking into account a 20% rate of lost to follow-up or non-evaluable patients, 58 patients should be included.
 
At the end of recruitment:
 
During analysis:
 
 - if 32 or fewer patients are alive without progression, then the treatment is considered ineffective - if 33 or more patients are alive without progression, then the treatment is considered effective 
The decision rule will be adjusted based on the actual number of evaluable patients.

Number of subjects needed	58
Associated translational studies	
 - On lipid parameters: The objective of this study will be to evaluate the impact of the different parameters of the lipid profile and the metabolism of lipoproteins on the response to treatment. - On Pathology: At the end of the study, if a sufficient number of patients have undergone secondary resections of liver metastases, a collection of surgical parts will be organized. An anatomopathological study of the tumor parenchyma and the healthy parenchyma resected after DEBIRI treatment will be performed.

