- If the following grade 3 or 4 toxicities occur as a result of chemoembolization, no additional session will be performed (but FOLFOX will be continued).

- Arteritis
- Grade 3 or 4 hepatic impairment
- Local ischemic and septic manifestations (cholecystitis, hepatic infarction, hepatic abscess, digestive hemorrhage) of grade 3 or 4
- Grade 3 or 4 renal insufficiency
- **The interval between chemoembolization sessions may be extended to allow for recovery of liver function.**
- No dose adjustment of irinotecan is planned for chemoembolization sessions.
- In case of hematological toxicity, FOLFOX dose adjustment rules **will be applied and chemoembolization will be continued.**

In case of doubt, do not hesitate to ask for advice from the study's referring radiologist, [name], through the FFCD.

VII. PATIENT MONITORING DURING TREATMENT AND AFTER WITHDRAWAL OF TREATMENT

Monitoring during treatment:

- **Before each cycle of FOLFOX:**
 - Complete clinical examination including: weight, vital signs, WHO, pain assessment (VAS)
 - Biological check-up: CBC/platelets
 - Adverse event evaluations according to NCI CTC version 4.0
- **Before each chemoembolization session**
 - Complete clinical examination including: weight, vital signs, WHO, pain assessment (VAS)
 - Biological workup consisting of measurements of hematological, nephrological and hepatic parameters: CBC/platelets, blood ionogram, creatinine, albumin, transaminases (AST, ALT), alkaline phosphatases (ALP), total and conjugated bilirubin, PT
 - Adverse event evaluations according to NCI CTC version 4.0

CEA and CA 19-9 assays, as well as thoracoabdomino-pelvic CT and liver MRI will be performed at an initial evaluation between D63 and D70 and then every 2 months after the start of treatment.

For patients participating in the associated 'lipid' translational study, please remember to perform the fasting sample and then technician the sample.

After the chemoembolization treatment period:

All patients will receive chemotherapy with FOLFOX every 2 weeks according to the usual regimen until progression or unacceptable toxicity.

VIII. STOP PROCESSING THE STUDY

The processing of the study will be stopped in case of:

- Investigator's decision
- Major toxicity requiring discontinuation of treatment (despite protocol adaptations)
- Serious or unexpected event requiring discontinuation of protocol treatment
- Progression of the disease
- Patient refusal or withdrawal of consent

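### The FOLFOX compliance ratio has no defined denominator and no time term, so delayed full-dose chemotherapy can read as 100%; per-drug relative dose intensity would show the delay

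*SAP*

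**What the plan says.** Protocol XII.2.2 makes tolerance a secondary endpoint, assessed among other things by "duration of treatment, doses received, dose reductions and deferrals". The SAP puts this into practice for FOLFOX in three places.

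- **SAP 7.5.2.2 (doses).** "Compliance will be calculated according to the formula": cumulative mg received, divided by the "theoretical protocol dose (in mg"), times 100, reported separately for each molecule. For the protocol dose it lists four figures per m², for example "Oxaliplatin = 85 mg/m²". It gives no number of cycles, no planned duration, no rule for body surface area (BSA), and no rule for cycles in which a molecule was omitted.
- **SAP 7.5.2.1 (duration).** The number of cycles per patient is reported. Duration runs from the start of the first treatment to the "Start date of last treatment", plus 1 day. "Therapeutic breaks and any deferral days during this period will not be subtracted from this duration".
- **SAP 7.5.2.3 (modifications).** Patients with at least one deferral, patients with at least one dose change, and patients who stopped for good are counted, with reasons.

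The regimen is open-ended. The Protocol synopsis says "FOLFOX will be administered every 2 weeks until progression or unacceptable toxicity", and Protocol VII repeats it for the time after chemoembolization: "All patients will receive chemotherapy with FOLFOX every 2 weeks according to the usual regimen until progression or unacceptable toxicity".

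**The concern.** A cumulative-dose ratio needs a cumulative plan. A regimen given until progression has none, so whoever programs the table must choose the denominator, and different choices give very different percentages from the same patient. Whichever number of cycles is chosen, the ratio compares amounts of drug and not amounts per unit of time, so a late cycle counts the same as one given on day 14.

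This matters because much of the toxicity in this regimen would appear as delay or as a dropped drug. Protocol VI.1 requires neutrophil and platelet recovery before a cycle resumes, and foresees stopping oxaliplatin or the 5-FU bolus for certain toxicities. Protocol VI.2 applies the FOLFOX adjustment rules for hematological toxicity while chemoembolization continues. A table headed compliance that reads about 100% could be taken to mean that systemic chemotherapy was delivered as planned when it was not.

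**Working it through.** The documents give no compliance or dose-intensity figure, so there is nothing to reproduce. The check applies the SAP's formulas to assumed patients. The spacings, stopping times and cycle totals are illustrations, not predictions.

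**Inputs from the documents.** Oxaliplatin 85 mg/m² per cycle (SAP 7.5.2.2; Protocol V.3); 14-day cycles; 1 month = 30.4375 days (SAP 6.2); in the 4-session schedule, cycle 5 at T+56 and session 4 at T+59 (Protocol V.3).

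**Formulas.** All amounts are in mg/m², as if BSA were constant.
- Compliance, reading A = dose received / (85 × cycles started).
- Compliance, reading B = dose received / (85 × a fixed number of cycles). I assume 20: 9 × 30.4375 = 273.9 days, which holds 20 cycle starts at 14-day spacing.
- Relative dose intensity (RDI) = (dose received / W) / (85 / 2), where W = (last start − first start + 14 days) / 7 weeks and 85 / 2 = 42.5 mg/m² per week.

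**1. Delay, 12 full-dose cycles (12 × 85 = 1020 mg/m²).** Compliance is 100% on reading A and 12/20 = 60% on reading B at every spacing.

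| Spacing | Days incl. last cycle | W (weeks) | mg/m² per week | RDI |
|---|---|---|---|---|
| 14 days | 11 × 14 + 14 = 168 | 24 | 42.50 | 100% |
| 17.5 days | 11 × 17.5 + 14 = 206.5 | 29.5 | 34.58 | 81.4% |
| 21 days | 11 × 21 + 14 = 245 | 35 | 29.14 | 68.6% |

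So neither reading responds to delay.

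**2. A drug dropped part-way.** Oxaliplatin in 8 of 16 on-time cycles: 8 × 85 = 680 mg/m². Dividing by its own 8 cycles gives 100%; dividing by all 16 FOLFOX cycles (1360 mg/m²) gives 50%. The SAP does not say which. RDI over all 16 cycles: W = (15 × 14 + 14) / 7 = 32 weeks, 680 / 32 = 21.25, and 21.25 / 42.5 = 50%.

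**3. Dose reduction.** Oxaliplatin at 65 instead of 85 mg/m² from cycle 5 of 12: (4 × 85 + 8 × 65) / 1020 = 860 / 1020 = 84.3% on reading A. Reductions therefore do show.

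**4. Early stopping.** Four on-time full-dose cycles: reading A 100%, reading B 4/20 = 20%, RDI = (340 / 8) / 42.5 = 100%. RDI does not reveal early stopping.

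**5. What duration shows.** For 12 cycles the SAP duration is 11 × 14 + 1 = 155 days (5.09 months) on time and 11 × 21 + 1 = 232 days (7.62 months) at 21-day spacing. Read beside the cycle count, it does reflect delay.

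**6. Window for the DEBIRI period.** Session 4 (T+59) follows cycle 5 (T+56), so any delay it causes falls on cycle 6, due at T+70. Suppose cycles 1 to 5 are on time at full dose (425 mg/m²) and cycle 6 starts a week late, at T+77. A window closed 14 days after cycle 5 gives (425 / 10) / 42.5 = 100%. A window running to the actual start of cycle 6 gives (425 / 11) / 42.5 = 90.9%.

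**The case against.** The strongest reply is that exposure is described by SAP 7.5.2.1 to 7.5.2.3 together, not by one ratio. Cycle counts, a duration that retains deferrals, and counts of deferrals, dose changes and discontinuations with reasons cover the protocol's list. Much of this stands, and it rules out three stronger readings that a reader might infer.

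- **That the planned summaries cannot show delay.** They can, indirectly: step 5 gives 155 against 232 days for the same number of cycles. What remains is narrower. Counting patients with at least one deferral treats one short delay like eleven week-long ones, length of delay is not summarised, and group summaries of duration and cycle count do not give intensity by patient or by drug.
- **That the duration rule produces the 100% figure.** Duration does not enter the compliance formula.
- **That duration is wrong by 13 days.** Ending at the last cycle start is a fixed, stated convention. Adding 14 days is another convention; it suits RDI because each dose is planned to cover 14 days, but it does not make the SAP's duration an error.

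It is also fair to say that cycles started is only the natural denominator, not the only possible one, so 100% is not certain. That supports the point about the undefined denominator rather than weakening it.

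Finally, the formal objectives list tolerance, not FOLFOX intensity; Protocol XIII mentions feasibility only in general terms. With one arm and no FOLFOX-alone comparator, no exposure measure could attribute delay to DEBIRI. That limits what RDI can claim, but not its value as a description of what was delivered.

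**Conclusion.** The point holds as a limited one. The compliance denominator is undefined for a regimen given until progression, and the ratio ignores time on either reading examined. On the cycles-started reading, full-dose FOLFOX reads 100% where RDI would be 81.4% (17.5-day spacing) or 68.6% (21-day spacing), and a drug omitted from half the cycles reads 100% or 50%. These sizes rest on assumed spacings applied to every cycle and on constant BSA; the documents give no expected delay. Dose reductions do show in the ratio, and delay shows indirectly elsewhere. The gap is the absence of any per-patient, per-drug intensity or length of delay. It concerns descriptive tolerance data and changes neither the primary endpoint nor the decision rule of 33 out of 48.

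**What to change.** In SAP 7.5.2.2, replace the compliance formula with relative dose intensity for each drug:

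(cumulative mg/m² received / weeks on FOLFOX) / (protocol mg/m² per cycle / 2)

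- **Dose received:** mg given at each cycle divided by the BSA recorded for that cycle, summed over cycles.
- **Weeks on FOLFOX:** from the first cycle start to the last FOLFOX cycle start plus 14 days. Every FOLFOX cycle counts for every drug, including cycles in which that drug was omitted.
- **Periods:** overall, and for the DEBIRI period from the start of cycle 1 to the start of cycle 6 (dose from cycles 1 to 5), or to the last cycle start plus 14 days if cycle 6 is not given. This captures delay after session 4.
- **Keep** the cycle counts in SAP 7.5.2.1 and the discontinuation summaries in SAP 7.5.2.3, because RDI does not show early stopping.

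The cost is SAP wording and a little programming. The SAP's own formulas already need the doses and cycle start dates, and Protocol VII has weight measured before each FOLFOX cycle. SAP 4.5 provides for adjustments, which must be made before the database is frozen. The downside is that the reported figure will probably look less favourable.
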